4.5.2 Plan for Review of Pauses and Resuming the Study

The IND Sponsor, with participation by the PI and PSRT, will conduct the review and make the decision to resume, amend or close the study and notify the IRB accordingly. As part of the pause review, the reviewers will also advise on whether the study needs to be paused again for any subsequent AEs of the same type. The pause criterion for the SAE will continue to apply.

The administration of study injections and new enrollments would resume only if review of the events that caused the pause resulted in a recommendation to permit further study injections and enrollments. Safety data reports and changes in study status will be submitted to relevant regulatory authorities in accordance with Section 5 and institutional policy.

5. SAFETY AND ADVERSE EVENT REPORTING

5.1 ADVERSE EVENTS

Adverse Event (AE) - Any untoward medical occurrence in a human subject, including any abnormal sign (for example, abnormal physical exam or laboratory finding), symptom, or disease, temporally associated with the subject's participation in research, whether or not considered related to the subject's participation in the research. In the context of FDA-required reporting, an AE means any untoward medical occurrence associated with the use of a drug in humans, whether or not considered drug related.

Each AE will be graded according to the Toxicity Grading Scale for Healthy Adult and Adolescent Volunteers Enrolled in Preventive Vaccine Clinical Trials, Food and Drug Administration Guidance – September 2007 ([Appendix II](#)). The following guidelines will be used to determine whether or not an AE is recorded in the study database:

- Solicited AEs (i.e., reactogenicity parameters as defined in [Section 4.2.6](#)) will be recorded without attribution assessments by the subject on paper or an electronic diary card for 7 days after each injection. If the paper diary card is completed by subject, data will be transcribed by a clinician into the study database. Clinicians will follow and collect resolution information for any reactogenicity symptoms that are not resolved within 7 days.
- All unsolicited AEs will be recorded with attribution assessments in the study database from receipt of the first study injection through completion of the 4 week visit that follows each study injection. At other periods between injections and following the 4 week post-injection visit after the second vaccination through the last study visit, only SAEs ([Section 5.2](#)), new chronic medical conditions, and influenza or ILI will be recorded.
- Cases of influenza or influenza-like illness (ILI) will be evaluated as follows:
ILI is defined as fever (temperature of 100°F [37.8°C] or greater) and a cough and/or sore throat in the absence of a known cause other than influenza. Collection of nasopharyngeal swabs will be used for laboratory confirmation of influenza by polymerase chain reaction (PCR) in subjects who meet criteria for ILI. The severity of illness in subjects with laboratory confirmed influenza illness will be recorded on a case report form rather than on an AE form.

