4.4.1 Discontinuation of Study Injections

A subject will be discontinued from receiving study product for the following reasons:

1. Subject voluntarily withdraws
2. Pregnancy
3. Grade 3 unsolicited AE assessed as possibly, probably or definitely related to study product
4. Grade 4 AE assessed as related to study product
5. Immediate hypersensitivity reaction associated with study product
6. Intercurrent illness that is not expected to resolve prior to the next scheduled study injection
7. Treatment with systemic glucocorticoids (e.g., prednisone or other glucocorticoid) or other immunomodulators (other than nonsteroidal anti-inflammatory drugs [NSAIDs]), with the exception that study injections may continue per investigator discretion if the next dose occurs at least 2 weeks following completion of glucocorticoid treatment

8. The study PI assesses that it is not in the best interest of the subject to continue the vaccination schedule

Group 2 subjects who do not receive the second injection as scheduled are expected to continue follow-up according to the Schedule of Evaluations for Group 1 subjects, except that research sample collections will be discontinued for pregnant women or others in which it is contraindicated.

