4.5 CRITERIA FOR PAUSING AND RESUMING THE STUDY

4.5.1 Plan for Pausing the Study

The PI and Protocol Safety Review Team (PSRT) will closely monitor and analyze study data as they become available and will make determinations regarding the presence and severity of AEs. The administration of study injections and new enrollments will be paused and the IND Sponsor will be promptly notified according to the following criteria:

- **One** (or more) subject experiences a **SAE** or **Grade 4 AE** assessed as related to study product.
- **Two** (or more) subjects experience the same **Grade 3 unsolicited AE** assessed as possibly, probably or definitely related to study product.
- **Three** (or more) subjects experience the same **Grade 2 or higher laboratory abnormality** assessed as possibly, probably or definitely related to study product.
- **One** (or more) subject experiences ulceration, abscess, or necrosis at the injection site.

Self-limited solicited reactogenicity that is not an SAE will not be counted towards pause criteria.

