6.4.6 Interim Analyses

Safety Reviews: The PSRT will review safety data routinely throughout the study. The study will utilize both electronic database features and reviews by designated safety review personnel to identify in a timely manner if any of the safety pause rules of the study are met.

Immunogenicity Review: Analyses of immunogenicity may be performed when pseudo-neutralization assay of samples collected 2 weeks after each vaccination are conducted. This may occur prior to completion of safety follow-up visits or collection of data for secondary and exploratory immunogenicity endpoints. Such an analysis would constitute the final analysis for the primary immunogenicity endpoint, so sample size adjustments are not required. Reports providing results by study group may be provided to VRC solely for the purpose of informing decisions related to future trials in a timely manner. The results should in no way influence the conduct of the VRC 321 trial in terms of early termination or later safety or immunogenicity endpoint assessments. Analyses of secondary and exploratory immunogenicity assays may also be performed as data become available.

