Research Samples																								
H. pylori ferritin antibody and human ferritin antibody	X				X								X											
Serum	32	16		16	16	16	16		16		16	16	16	16	16	16	16							
PBMC and plasma	80	80		80	80	80	80		80		80	⁷ 120 or Apheresis (6)	80	80	80	80	80							
Daily Volume (mL)	122	103	0	96	103	103	96	103	103	0	96	136	103	116	103	103	103							
Max. Cumulative Volume (mL)	122	225	225	321	424	527	623	726	727	822	958	1,061	1,177	1,280	1,383	1,486	1,486							

* VRC 500: Screening evaluations must be no more than 28 days prior to Day 0 to be used for eligibility (pregnancy test from Day 0 must be used for eligibility). If clinical assessment on Day 0 suggests significant changes may have occurred since screening, then physical examination & laboratory studies done on Day 0 are used for eligibility.

¹ Day 0=day of enrollment and first vaccine injection. Day 0 evaluations prior to first injection are the baseline for assessing adverse events subsequently.

² Screening visit includes physical exam with vital signs. At other visits, physical examination is done if indicated. Otherwise only blood pressure (BP), pulse, temperature, and respiration are required.

³ Study Product Administration: Groups 2A-2D will receive H1ssF_3928 60 mcg IM at Day 0 and Week 16. Complete post vaccination evaluations (BP, pulse, temperature, respiration and injection site assessment) at 30 minutes or longer after each injection for Group 2A-2D.

⁴ Negative pregnancy test results must be confirmed for women of reproductive potential prior to each study injection and prior to apheresis.

⁵ HLA type blood sample is collected once at any time-point in the study and is shown as a Visit 05 evaluation for convenience; however, if HLA type is already available in the medical record, it does not need to be repeated. HLA type may also be obtained from a frozen sample.

⁶ Visit 03: Two EDTA tubes for PBMC collected will be sent to Building 40, while the remainder of the blood collected will be sent to VIP.

⁷ If optional Apheresis occurs, ONLY draw 16 mL in SST (DO NOT draw 120 mL in EDTA tubes).

⁸ For women of reproductive potential, pregnancy test must be negative within 72 hours prior to apheresis procedure.

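### Full adverse event recording lapses for 84 of the 112 days before dose 2, while the stop and pause rules that use those events have no time limit

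*Combined protocol and SAP*

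**What the plan says.** The recording rules in Section 5.1 are introduced by "The following guidelines will be used to determine whether or not an AE is recorded in the study database", so they govern database entry. Unsolicited AEs are entered with attribution "from receipt of the first study injection through completion of the 4 week visit that follows each study injection". Outside those windows the rule is "At other periods between injections and following the 4 week post-injection visit after the second vaccination through the last study visit, only SAEs", followed by "new chronic medical conditions, and influenza or ILI will be recorded". The AE definition at the head of the same section takes in abnormal laboratory findings.

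Two sets of rules use such events:

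- Section 4.4.1 ends a subject's injections for a "Grade 3 unsolicited AE assessed as possibly, probably or definitely related to study product", and separately for a related Grade 4 AE.
- Section 4.5.1 pauses injections and enrolment for one related SAE or Grade 4 AE, for two subjects with the same related Grade 3 unsolicited AE, and when three or more "subjects experience the same Grade 2 or higher laboratory abnormality assessed as possibly, probably or definitely related to study product".

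Neither section sets a time limit. On how a met pause rule is noticed, Section 6.4.6 says: "The study will utilize both electronic database features and reviews by designated safety review personnel". The dosing interval is in Appendix I: "Groups 2A-2D will receive H1ssF_3928 60 mcg IM at Day 0 and Week 16".

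In Section 6.2.1, the primary AE endpoint (all severities) uses the same 4-week window. The primary laboratory endpoint, change from baseline, has no such limit.

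**The concern.** The stop and pause rules turn on a grade and a relatedness judgement, and two of the pause rules also need a count of the same event in different subjects. Section 5.1 requires an AE record with attribution only inside the 4-week windows. For a non-serious event with onset in Weeks 4-16, the documents do not say how it comes to be graded, attributed and counted.

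This is a first-in-human vaccine, and the affected interval is the one that precedes re-exposure. The earlier ferritin-vaccine study summarised in Section 1.3.1 shows that attribution matters. Anaemia was reported in 8 of 47 subjects, with a maximum of Grade 2 in five, which is more than the three-subject laboratory count used here. Yet anaemia is not among the three AEs listed there as related. Whether such a cluster counts depends on an attribution that Section 5.1 does not require for a finding at Visit 07.

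The second concern is the dose-2 AE table. Appendix I makes Day 0 the baseline for judging later AEs. An abnormality already present on the Visit 07 sample, and still present at Visit 10, could therefore first be entered as an AE after dose 2.

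**Working it through.** **Time before dose 2 (Groups 2A-2D).** Inputs from Appendix I: Visit 05 = Day 28, Visit 07 (dose 2) = Day 112, Visit 10 = Day 140, Visit 14 = Day 476.

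- Restricted recording before dose 2: 112 − 28 = 84 days; 84/112 = 75%.
- Visit windows: Visit 05 is ±2 days. No Visit 07 window is given for Group 2, so I assume the ±7 days given for Group 1. The extremes are (105 − 30)/105 = 71% and (119 − 26)/119 = 78%.
- After Week 20: 476 − 140 = 336 days.
- Full recording over the whole study: 28 + 28 = 56 of 476 days, or 12%.

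**Where the safety bloods fall.** The columns of the Group 2 table are not reliably aligned in the text available, so I used the tube volumes: serum 16 mL, PBMC and plasma 80 mL, CBC 3 mL, liver panel 4 mL.

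| Visit (day) | Daily volume (mL) | Safety bloods | Full AE window |
|---|---|---|---|
| 04 (14), 05 (28) | 103 = 16+80+3+4 | yes | inside |
| 06 (84) | 96 = 16+80 | no | outside |
| 07 (112), before dose 2 | 103 = 16+80+3+4 | yes | outside |
| 08 (118) | 96 = 16+80 | no | inside |
| 09 (126) | 136 = 16+120 | no | inside |
| 10 (140) | 103 = 16+80+3+4 | yes | inside |
| 11 (196) | 116 = 16+80+20 (HLA) | no | outside |
| 12, 13, 14 (280, 364, 476) | 103 = 16+80+3+4 | yes | outside |

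There are seven post-injection safety draws, at Visits 04, 05, 07, 10, 12, 13 and 14. Four fall outside the window (07, 12, 13, 14), but only Visit 07 precedes a subject's own dose 2. No safety bloods are scheduled between Day 28 and Day 112.

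**What the database alone would hold (illustration).** For n = 48 and a true rate p of one related Grade 3 AE before dose 2, let f be the share of onsets that fall inside the recording window, and q = p × f. The chance that two or more are in the database is 1 − (1−q)^48 − 48q(1−q)^47. With p = 0.05 and f = 1 this gives 0.699, which reproduces Table 6-1. The documents give no value for f, so it is an assumption:

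| f | q | Chance of two or more in the database |
|---|---|---|
| 1 | 0.05 | 0.699 |
| 0.9 | 0.045 | 0.642 |
| 0.5 | 0.025 | 0.338 |
| 0.25 (uniform onset over 112 days) | 0.0125 | 0.121 |

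These figures describe database content only. They are not the chance that the study would pause, because personnel review also feeds that decision.

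**The case against.** The strongest reply is that Section 5.1 limits database entry and nothing else. The investigator decides on stopping injections (Section 4.4). The investigator and safety review team monitor data as they arrive (4.5.1). Pause detection uses personnel as well as the database (6.4.6), and clinical data are reviewed daily (8.8.1). Potential reactions are evaluated before the schedule continues (4.2), and each subject is assessed on the injection day (4.2.5). Dose 2 can also be withheld for unresolved intercurrent illness or on the investigator's judgement, without an AE form.

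All of that stands. A reader might infer that the rules cannot see events in Weeks 4-16; the documents do not support this. A reader might also infer that laboratory abnormalities go unrecorded. They do not: values are measured, feed a primary endpoint (6.2.1) and are plotted throughout (6.4.3). What lapses is the required entry as a graded, attributed AE. A severe laboratory finding may also be judged an SAE under Section 5.2 and be recorded at any time.

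Other limits stand too. The 75% is calendar time, not share of risk. The continuation review in Section 4.3 takes place two weeks after the third subject's vaccination and is unaffected. The AE window matches the primary endpoint, so it looks deliberate. Misdating a persisting abnormality is possible, not inevitable: the Visit 07 value is on file, and AE listings show onset.

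This does not close the gap, because most of these safeguards work subject by subject. The weekly team review uses summary safety reports, and nothing says that these include events kept out of the database. No section requires such events to be graded, attributed or counted across subjects. A window suited to an endpoint also does not define the scope of the safety rules.

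**Conclusion.** The point holds as a mismatch between sections. For 84 of the 112 days before dose 2 (75%; 71% to 78% across visit windows), non-serious events other than new chronic conditions and influenza or ILI have no required AE record or attribution. Sections 4.4.1 and 4.5.1 act on such events with no time limit. The cross-subject pause counts are therefore not assured for events in Weeks 4-16 or for abnormalities on the Visit 07 bloods, and the dose-2 AE table could take in findings that began before dose 2.

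After Week 20 a Group 2 subject has no further injection, so that gap matters only for pausing other subjects still being enrolled or dosed. It would be wrong to cite four of seven safety draws as lost to the second-injection decision; one of them, Visit 07, bears on it. Even there, Section 4.2.5 explicitly requires only pregnancy results before the injection, so an AE form would not by itself protect that subject's dose on the day.

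This rests on three assumptions: full recording restarts at dose 2, which Section 5.1 implies but does not state; safety-blood visits are read correctly from the volumes; and the standard operating procedures mentioned in Section 8.8.1, which are not among the documents, do not already supply the missing requirement.

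**What to change.** Reconcile Section 5.1 with Sections 4.4.1 and 4.5.1, so that the text says how non-serious events outside the 4-week windows reach the rules that use them. As a data-recording change, have Section 5.1 also record with attribution, from each subject's first injection to 4 weeks after the last, the event types and grades that those two sections already name. This should include findings on the Visit 07 bloods. List these events separately, by onset relative to dose 2, so that they do not enter the dose-2 table as new.

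Leave the stopping and pause criteria and the primary all-severities endpoint unchanged. The cost is protocol wording and a few more AE forms. No visit or test is added: interim history is already taken at Visits 06 and 07, and the Visit 07 bloods are already drawn.

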5.2 SERIOUS ADVERSE EVENTS

The term “Serious Adverse Event” (SAE) is defined in 21 CFR 312.32 as follows: “An adverse event or suspected adverse reaction is considered serious if, in the view of either the investigator or the sponsor, it results in any of the following outcomes: Death, a life-threatening adverse event, inpatient hospitalization or prolongation of existing hospitalization, a persistent or significant incapacity or substantial disruption of the ability to conduct normal life functions, or a congenital anomaly/birth defect. Important medical events that may not result in death, be life-threatening, or require hospitalization may be considered serious when, based upon appropriate medical judgment, they may jeopardize the patient or subject and may require medical or surgical intervention to prevent one of the outcomes listed in this definition. Examples of such medical events include allergic bronchospasm requiring intensive treatment in an emergency

room or at home, blood dyscrasias or convulsions that do not result in inpatient hospitalization, or the development of drug dependency or drug abuse.”

“Life-threatening” refers to an AE that at occurrence represents an immediate risk of death to the subject. It does not include an AE or suspected adverse reaction that, had it occurred in a more severe form, might have caused death. Similarly, a hospital admission for an elective procedure is not considered a SAE.

5.3 ADVERSE EVENT REPORTING TO THE IND SPONSOR

AEs that meet SAE criteria must be reported and submitted by the clinical site on an expedited basis to the IND Sponsor, VRC/NIAID/NIH, according to sponsor guidelines as follows:

- Results in death;
- Is life threatening (places the subject at immediate risk of death from the event as it occurred);
- Results in inpatient hospitalization or prolongation of existing hospitalization;
- Results in persistent or significant disability/incapacity;
- Results in a congenital anomaly/birth defect in the offspring of a study subject; OR
- Based upon appropriate medical judgment, may jeopardize the subject’s health and may require medical or surgical intervention to prevent one of the other outcomes listed in this definition (examples of such events include allergic bronchospasm requiring intensive treatment in the emergency room or at home, blood dyscrasias or convulsions that do not result in inpatient hospitalization, or the development of drug dependency or drug abuse).

In addition, any event, regardless of severity, which in the judgment of an investigator represents a SAE, may be reported on an expedited basis.

An investigator must communicate an initial SAE report within 24 hours of site awareness of occurrence to the IND Sponsor data entry into the database, which triggers an alert to the IND Sponsor MO. Within 3 working days, a written summary by the investigator should be submitted to the IND Sponsor.

In order for the IND Sponsor to comply with regulations mandating sponsor notification of specified SAEs to the FDA within 7 or 15 calendar days, the investigator must submit additional information as soon as it is available.

5.3.1 IND Sponsor Reporting to the FDA

The IND Sponsor is responsible for making the determination of which SAEs are “serious and unexpected suspected adverse reactions” (SUSARs) as defined in 21 CFR 312.32. The following definitions apply:

- *Suspected adverse reaction* means any AE for which there is a reasonable possibility that the study product caused the AE.
- *Unexpected Adverse Event* means an AE that is not listed in the IB or is not listed at the specificity or severity that has been observed.

All SUSARs (as determined by the IND Sponsor) will be reported to the FDA as IND Safety Reports per 21 CFR 312.32 as soon as possible but not exceeding 7 calendar days for unexpected

fatal or life-threatening events, and not exceeding 15 calendar days for other qualifying events. IND Safety Reports will also be provided to the IRB.

The IND Sponsor will also submit an IND Annual Report of the progress of the investigation to the FDA as defined in 21 CFR 312.33.

5.4 REPORTING TO THE INSTITUTIONAL REVIEW BOARD

The following information is consistent with NIH IRB Policy 801: Reporting Research Events, Version 1, effective July 1, 2019.

Reportable Event - An event that occurs during the course of human subject research that requires notification to the IRB.

For the purposes of this policy, reportable events include the following:

- Unanticipated Problems (UPs) involving risks to subjects or others
- Non-compliance (including major protocol deviations and noncompliance that is not related to a protocol deviation)
- Deaths related or possibly related to research activities
- New information that might affect the willingness of subjects to enroll or continue participation in the study

5.4.1 Unanticipated Problem

An unanticipated problem (UP) is defined as any incident, experience, or outcome that meets all three of the following criteria:

- Unexpected (in terms of nature, severity, or frequency) given (a) the research procedures that are described in the protocol-related documents, such as the IRB approved research protocol and informed consent document; and (b) the characteristics of the subject population being studied; and
- Related or possibly related to participation in the research (possibly related means there is a reasonable possibility that the incident, experience, or outcome may have been caused by the procedures involved in the research); and
- Suggests that the research places subjects or others (which may include research staff, family members or other individuals not directly participating in the research) at a greater risk of harm (including physical, psychological, economic, or social harm) related to the research than was previously known or expected.

A UP must be reported within 7 calendar days of an investigator becoming aware of the actual or suspected UP.

